3.4.2 Demographics and Baseline Characteristics

Enrollment will be summarized by treatment group for each season using the respective ITT population.

- Season 1: Enrollment will be summarized by hemisphere, country, site, and by hemisphere, country, and age at randomization stratum. The total number of subjects randomized into each treatment group will be used as the denominator. For the summary of hemisphere, country, and age at randomization stratum, the number of mis-stratified subjects (ie, subjects whose age stratum as calculated from the eCRF do not match the IWRS database) will also be summarized. These summaries will be provided for each cohort (pre-term, CHD/CLD) as well as for all subjects combined.
- Season 2: Similar summary as described above for Season 1 will be provided for all subjects enrolled in Season 2.

Demographic characteristics will be summarized by treatment group using the respective ITT population:

- Season 1: Summary of demographic characteristics including gender, age at randomization (months) calculated from the CRF, age at randomization category determined using the CRF age calculation (age ≤ 3.0 months, age > 3.0 to ≤ 6.0 months, age > 6.0 months), GA (weeks), GA category (< 29 weeks, ≥ 29 weeks to < 32 weeks, ≥ 32 weeks to < 35 weeks, ≥ 35 weeks), ethnicity, race, weight (kg) on Day 1, weight on Day 1 category (weight < 5 kg, weight ≥ 5 kg), birth weight (kg), birth weight category (≤ 2.5 kg, > 2.5 kg), multiple birth (yes/no), siblings enrolled in the study (yes/no), ever breastfed (yes/no), currently breastfed (yes/no), smoking in the household (yes/no), currently in daycare (yes/no), underlying lung disease (yes/no), CHD (yes/no), CLD (yes/no), Down syndrome (yes/no), family history of atopy (including asthma, hay fever, eczema, wheezing) will be provided for each cohort (pre-term, CHD/CLD) and for all subjects. Subjects will be excluded from the summary (eg, means and percentages) of an individual parameter if data are missing. The summaries will also be provided for each age at randomization category and by hemisphere category.
- Season 2: Similar summary as described above for Season 1 will be provided for all subjects enrolled in Season 2. In addition, weight on Day 1, Season 2 will be summarized, and the corresponding weight on Day 1, Season 2 category will be: weight < 7 kg, weight ≥ 7 kg for safety subgroup analysis; weight < 10 kg, weight ≥ 10 kg for efficacy subgroup analysis. Demographic and baseline characteristics will also be summarized for CHD subjects and CLD subjects separately for each season. If a subject has both CHD and CLD, the subject will be included in both summary tables.

3.4.3 Study Drug Exposure

Summaries will be presented by treatment group for each season as well as for the two consecutive seasons using the respective as-treated population.

- Season 1: Summary of study drug exposure will include the number of doses received, number of active doses received, cumulative number of doses received (ie, at least 1, at least 2, etc.), cumulative number of active doses received, the number of subjects receiving planned volume of doses, the number of subjects receiving planned active doses, the number of subjects receiving at least 1 dose out of window (2-day and 7-day window will be considered), the number of subjects missing at least 1 dose. These summaries will be provided for each cohort (pre-term, CHD/CLD) and for all subjects combined.
- Season 2: Similar summary as described above for Season 1 will be provided for all subjects enrolled in Season 2 and the reporting period will be Day 1, Season 2 through Day 151, Season 2.
- Season 1 + Season 2: Similar summary as described above for Season 1 will be provided for all subjects enrolled in Season 2 and the reporting period will be Day 1, Season 1 through Day 151, Season 2.

In addition, subjects who have received mixed dose of investigational product will be listed.

3.4.4 Violations and Deviations

Important protocol deviations are a subset of protocol deviations that may significantly impact the completeness, accuracy, and/or reliability of the study data or that may significantly affect a subject's rights, safety, or well-being.

The final list of important protocol deviations will be documented prior to unblinding the study data, and will include but may not be limited to:

- Subjects who did not meet inclusion criteria or met exclusion criteria according to protocol but were enrolled in the study, except for one violation of the exclusion criterion that children of employees of the sponsor, clinical study site, or any other individuals involved with the conduct of the study, or immediate family members of such individuals will not be considered as an important protocol deviation.
- Subjects who reported investigational product (IP)-related deviations. This can be further categorized into IP administration-related deviations, IP assignment-related deviations, IP handling-related deviations, and IP compliance-related deviations.
 - IP administration-related deviations include but are not limited to:
 - o Not getting subsequent IP doses after initial dose;

- Failure to discontinue IP despite withdrawal of consent or not meeting eligibility prior to dosing;
- IP assignment-related deviations include but are not limited to:
 - o Inappropriate use of study IP (eg, giving IP to non-study subjects);
 - Incorrect IP dispensed to subject (eg, IP assigned via IWRS was different from IP dispensed to subject);
 - Kit dispensed without IWRS transaction
- IP handling-related deviations include but are not limited to:
 - O Dispensing of IP which had an unapproved temperature excursion or was not suitable for use upon inspection for whatever reason to a subject;
 - o IP was administered to the subject after 4 hours post preparation
- IP compliance-related deviations include but are not limited to:
 - O Subject was administered IP but was not observed for at least 1 hour post dose;
 - Subject did not get replacement dose (at all or as soon as possible after cardiac bypass surgery)
 - Wrong dose of IP given
- Subjects who had no central RT-PCR RSV nasal sample collected for any of the LRTI visits
- Subjects who reported safety-related deviations:
 - Severe violation in safety follow-up for subject
 - Serious adverse event not reported in eCRF.

Only important protocol deviations will be tabulated in the clinical study report (CSR). The important protocol deviations will be reviewed and documented by the medical advisors and statisticians prior to the DBL.

Protocol deviations associated with the COVID-19 pandemic will also be summarized and listed separately (see Section 3.10).

3.4.5 Medical History

Medical history data will be summarized as number (%) of subjects by treatment, according to Medical Dictionary for Regulatory Activities (MedDRA) System Organ Class (SOC) and Preferred Term (PT) categories. If a subject has more than 1 record in a specific category, the subject will be counted only once for the category. The denominators for calculating percentages will be based on the number of subjects in the AT population for each treatment group.

In addition, medical history findings which are ongoing at the time of signed informed consent will be also summarised by treatment.

The Season 1 medical history summaries will also be provided for each cohort (pre-term, CHD/CLD), CLD subjects, CHD subjects, subjects with GA < 29 weeks, subjects with GA < 29 weeks and without CLD or CHD, and CLD subjects with GA < 32 weeks. The Season 2 medical history summaries will also be provided for CLD subjects, CHD subjects, and CLD subjects with GA < 32 weeks.

3.5 Efficacy Analyses

The analyses of the efficacy endpoints, including the incidence of protocol-defined medically attended RSV LRTI (also described as the medically attended RSV LRTI) through 150 days post 1st dose, as well as the incidence of protocol-defined RSV hospitalization (also described as the RSV LRTI hospitalization) through 150 days post 1st dose, will be performed on the respective ITT population for Season 1 and 2. The incidence will be calculated as the proportion of subjects who meet the endpoint during the reporting period. Only summaries will be provided for the efficacy analyses unless specified otherwise. The summaries will be based on observed events.

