4.1.5 Withdrawal from the Study

Subjects may at any time be withdrawn from the study without prejudice to further treatment (withdrawal of consent). The caregivers of such subjects will always be asked about the reason(s) for withdrawal and the presence of any AEs. If possible, the subject will be seen and assessed by the investigator. AEs will be followed up. If a subject withdraws from further participation in the study, then no further study visits or data collection should take place.

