4.1.6 Discontinuation of Investigational Product

An individual subject will not receive additional doses of study drug, including continued dosing in Season 2 for subjects with CLD/CHD, if any of the following occur in the subject in question:

- 1 Withdrawal of consent
- 2 Hypersensitivity reaction assessed as related to study drug

Subjects who have received any study drug will be followed for protocol-specified assessments including follow-up of any AEs unless consent is withdrawn specifically from further study participation (Section 4.1.5) or the subject is lost to follow-up. Subjects who have not received study drug, regardless of reason, will not be followed.

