4.8 Statistical Evaluation

4.8.1 General Considerations

Tabular summaries will be presented by treatment group. Categorical data will be summarized by the number and percentage of subjects in each category. Continuous variables will be

summarized by descriptive statistics. Additional details of statistical analyses will be described in the statistical analysis plan.

The Intent-to-treat (ITT) Population is defined as all randomized subjects, analyzed according to randomized treatment assignment. All efficacy analyses will be performed on the ITT Population.

The As-treated Population (ATP) is defined as all subjects who receive any investigational product, analyzed according to treatment received. All analyses, with the exception of efficacy, will be performed on the ATP unless otherwise specified.

A primary analysis, Season 2 analysis, and final analysis are planned for the study. The primary analysis will be conducted after all randomized subjects have completed follow-up through the first 5-month RSV season (ie, Season 1 Day 151 visit) and include all available Season 1 safety, efficacy, PK, and ADA data at the time of the data cutoff. Season 2 analysis will be conducted after all the CLD/CHD subjects have completed follow-up through the second 5-month RSV season (ie, Season 2 Day 151 visit) and include all available Season 1 data and Season 2 safety, efficacy, PK, and ADA data at the time of the data cutoff. The final analysis will be conducted when all subjects have completed the last visit of the study and include all data collected in the study.

At the time of the primary analysis, the Season 1 data will be unblinded to the Sponsor/designated clinical research organization associated with the analysis, write-up, and regulatory submission.

To ensure the blinding of Season 2 treatment assignment for CLD/CHD subjects who were randomized to the palivizumab arm in Season 1, any data with potential unblinding risk will be split by Season 1 and Season 2 by the corresponding third party data vendors and when the primary database lock occurs, only unblinding data from Season 1 will be transferred to the Sponsor for analysis.

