4.8.4 Efficacy

The primary efficacy endpoint is the incidence of medically attended RSV LRTI (inpatient and outpatient) through 150 days post Dose 1 (ie, during a typical 5-month RSV season) in Season 1. The determination of the primary efficacy endpoint will be based on RSV test results (performed centrally using real-time RT-PCR; see Section 4.3.1.2) and objective protocol-defined LRTI criteria (see Table 7 and Table 8), and will be summarized by Season 1

treatment group for all 900 subjects. The 95% CI of the percentage of subjects meeting the primary efficacy endpoint will be presented by treatment group. For subjects with multiple medically attended RSV LRTI events, only the first occurrence will be used in the primary efficacy summary.

In addition, the summary of incidence of RSV LRTI through 150 days post Dose 1 in Season 2 will be provided for the 300 subjects in the CLD/CHD cohort based on the treatment assignments through Season 1 and Season 2: ie, (a) 50 mg MEDI8897 for infants with body weight < 5 kg and 100 mg MEDI8897 for infants with body weight \geq 5 kg (Season 1)/200 mg MEDI8897 (Season 2), (b) palivizumab (Season 1)/200 mg MEDI8897 (Season 2), and (c) palivizumab (Season 1)/palivizumab (Season 2).

The incidence of RSV hospitalization through 150 days after dosing (ie, during the 5-month RSV season) will be summarized by treatment group using a similar strategy as described above for RSV LRTI.

Additional analyses will include summarizing RSV-positive LRTI endpoints using results from either the central laboratory or local laboratory.

All efficacy summaries will be based on the ITT Population.

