3.2 Analysis Populations

The analysis populations are defined in Table 1.

Table 1Analysis Populations

Population	Description	
Intent-to-treat (ITT)	The ITT population (Season 1) includes all subjects randomized in Season 1. In this population, subjects will be analyzed according to their randomized treatment group in Season 1.	
population (Season 1)	The analysis for baseline/demographic characteristics, efficacy and HRU for Season 1 will be performed on this population.	
Intent-to-treat (ITT)	The ITT population (Season 2) includes all CHD/CLD subjects enrolled in Season 2. In this population, subjects will be analyzed according to their randomized treatment group through the two seasons (ie, in Season 1 and in Season 2).	
population (Season 2)	The analysis for baseline/demographic characteristics, efficacy, and HRU for Season 2 and/or through the two seasons (Season 1 + Season 2), will be performed on this population.	
	The As-treated population (Season 1) includes subjects who receive any investigational product in Season 1. In this population, subjects will be analyzed according to the actual treatment received in Season 1.	
	The analysis for safety, PK, ADA, serology, and RSV neutralizing antibody for Season 1 will be performed on this population.	
As-treated population	For subjects who accidentally receive both MEDI8897 and palivizumab in Season 1:	
(Season 1)	- For summaries on safety, subjects who receive any amount of MEDI8897 will be included in the MEDI8897 group.	
	 For summaries on PK, ADA, serology, and RSV neutralizing antibody, subjects will be analyzed according to the first dose they receive. The data collected up to the point of dose switch will be included in the summaries. All the data collected afterwards will be presented in the listing. 	
	The As-treated population (Season 2) includes subjects who receive any study investigational product in Season 2. In this population, subjects will be analyzed according to the actual treatment received through the two seasons (ie, in Season 1 and in Season 2).	
As-treated population (Season 2)	The analysis for safety, PK, ADA, serology, and RSV neutralizing antibody for Season 2 and/or through the two seasons (Season 1 + Season 2), will be performed on this population.	
	For subjects who received mixed doses of investigational product, similar rules as described above for Season 1 will be applied for Season 2.	

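### The 150-day RSV incidences count infants who leave without a recorded event as event-free; add a Day-150 time-to-event estimate beside the crude proportion

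*SAP*

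**What the plan says.** SAP 3.5 analyses both efficacy endpoints on the ITT population. "The incidence will be calculated as the proportion of subjects who meet the endpoint during the reporting period", and "The summaries will be based on observed events".

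The denominator is everyone randomised. SAP 3.2 states: "The ITT population (Season 1) includes all subjects randomized in Season 1". Protocol 4.8.4 likewise summarises the primary efficacy endpoint by Season 1 "treatment group for all 900 subjects". SAP 3.5.1.1 attaches a Clopper-Pearson 95% interval to each arm's percentage.

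Two follow-up rules matter. After withdrawal, Protocol 4.1.5 says that "no further study visits or data collection should take place". Protocol 4.1.6 says: "Subjects who have not received study drug, regardless of reason, will not be followed".

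No censoring, person-time or outcome-imputation rule covers incomplete follow-up. SAP Appendices 4 and 5 impute dates only, and the time-to-first-event item in 3.5.1.1 is a plot of individual infants along an age axis. For events after Day 150, SAP 3.5.3 and 3.6.6 do restrict the denominator to infants still in the study at the Day 151 visit.

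SAP 3.5.1.3 plans a sensitivity analysis of RSV LRTI that drops infants with a wrong treatment, a missed active dose or an active dose outside a 7-day window. SAP 3.10 plans a similar one for doses missed or delayed because of COVID-19. SAP 3.4.1 tabulates disposition by arm, including infants randomised but not treated and status at Day 151.

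**The concern.** An infant who leaves on Day 40 with no event has been observed for 40 days but enters the table as 150 days without RSV disease. An infant who is never dosed has no follow-up at all, and a window that starts at the first dose has no starting point for that infant. The numerator can lose events to missing follow-up while the denominator loses nobody, so the bias in each arm is downward. The binomial interval reflects none of this.

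There is no hypothesis test for efficacy, so the per-arm percentages and their intervals are this trial's efficacy readout. If more infants leave one arm than the other, or if leaving is related to RSV risk, part of any visible difference would come from follow-up and not from the drugs. The SAP recognises this kind of problem in 3.5.1.2, where it warns of bias if Season 1 dropouts are associated with efficacy.

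**Working it through.** **1. The plan's own figures.** SAP 2.4 assumes a 6% rate: 300 × 0.06 = 18 and 600 × 0.06 = 36 events. Both reproduce, and both allow for no loss.

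**2. Expected crude proportion.** Neither document gives a dropout rate, so loss is an assumption. Let a share *d* of infants leave evenly over 150 days, with a constant hazard and true 150-day risk *p*. With L = −ln(1 − p), a leaver has on average a recorded event before leaving with probability 1 − (1 − e^−L)/L. For p = 6%, L = 0.061875 and this is 1 − 0.06/0.061875 = 3.03%. The expected crude figure is (1 − d)p + d × 3.03%.

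- d = 5%: 5.70% + 0.15% = 5.85%
- d = 10%: 5.40% + 0.30% = 5.70%
- d = 20%: 4.80% + 0.61% = 5.41%

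| Leave before Day 151 | Crude, true 6% | Events in 600 / 300 | Crude, true 1.9% (hospitalization) |
|---|---|---|---|
| 0% | 6.00% | 36.0 / 18.0 | 1.90% |
| 5% | 5.85% | 35.1 / 17.6 | 1.85% |
| 10% | 5.70% | 34.2 / 17.1 | 1.81% |
| 20% | 5.41% | 32.4 / 16.2 | 1.71% |

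**3. Never-dosed infants (Season 1).** Protocol 1.4.1 gives 1,453 randomised and 1,447 dosed in the Phase 2b study: 6/1,453 = 0.41%. At that share the effect is 0.41% × 6%, about 0.025 percentage points. With an assumed 1% undosed and 10% leaving, the crude figure is 0.99 × 5.70% = 5.65%.

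**4. Between arms, equal true risk of 6%.** Equal loss unrelated to risk leaves the ratio of the two percentages essentially unchanged. With 5% loss on MEDI8897 and 15% on palivizumab, the figures are 5.85% and 5.55%, a ratio of 1.05. Reversing the losses gives 0.95.

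**5. The set in SAP 3.5.1.3, with 10% uniform loss in both arms.** Assume that a dose scheduled after an infant has left counts as missed. MEDI8897 has one active dose, on Day 1, so every later leaver stays in: 5.70%. Palivizumab has active doses up to Day 121, so the 120/150 = 80% of leavers who go before Dose 5 drop out. That leaves 0.90 completers and 0.02 late leavers. The late leavers' average risk is about 1 − exp(−0.061875 × 135/150) = 5.42%. The result is (0.90 × 6% + 0.02 × 5.42%)/0.92 = 5.99%. Equal true risk thus appears as 5.70% against 5.99%, a small artefact in favour of MEDI8897.

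**6. The interval.** The exact 95% CI is 4.2% to 8.2% for 36/600 and 3.6% to 9.3% for 18/300. Its coverage of the true 6% in the 600-infant arm is 96.1% with full follow-up, 95.0% with 1% undosed and 10% leaving, and 91.8% with 1% undosed and 20% leaving.

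**7. The alternative estimator.** In 4,000 simulated arms of 600, one minus Kaplan-Meier at Day 150 averaged 6.00% (5% leaving, none undosed), 5.99% (10%, 1%) and 6.00% (20%, 2%). The expected crude figures are 5.85%, 5.65% and 5.30%. Loss was unrelated to risk in these simulations.

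**The case against.** The strongest reply is that the rule is stated openly, its effect is small, and no decision rests on it. The primary objective is safety. Efficacy is secondary and descriptive, with no test or margin, and SAP 1 and 3.9 place the supporting efficacy argument in a separate PK extrapolation plan. At 5% loss the shift is 0.15 percentage points inside an interval about 4 points wide. Protocol 4.1.6 keeps following infants who stop study drug. Protocol 4.6.1 requires dosing on the day of assignment, so few infants should go undosed. The counts in SAP 3.4.1 let a reader see the loss in each arm. The set in 3.5.1.3 already removes never-dosed infants from the RSV LRTI analysis. Kaplan-Meier brings its own untestable assumption.

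All of this stands as a limit on size. It does not remove the point. The disposition counts are not split by event status and do not sit beside the endpoint. The set in 3.5.1.3 keeps MEDI8897 leavers as event-free, removes most palivizumab leavers, and does not cover RSV hospitalization. The set in 3.10 also selects on doses.

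Two alarming comparisons might be drawn, and neither is a fair measure of the problem. At 5% loss about 29.1 of 600 MEDI8897 infants leave without an event. Counting them all as events gives (35.1 + 29.1)/600 = 10.7%, but that requires every one of them to fall ill against a 6% background, and Kaplan-Meier would not address that scenario either. At a 1% rate, 30 leavers would outnumber 6 events, yet only about 0.15 events would be expected to go unseen among them. The plan says rates could be much lower; it does not predict 1%.

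**Conclusion.** The point holds as a cheap improvement, not as a flaw that invalidates the efficacy summary. Over 5% to 20% uniform loss the relative understatement is about 2.5% to 10%. It reaches about 12% if 2% are also undosed. These sizes rest on assumed loss, a constant hazard and a 6% risk; the direction within each arm does not depend on those values.

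The documents do not support three stronger readings that a reader might infer:

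- That every leaver is scored event-free. An infant with a recorded event before leaving is counted.
- That the comparison between arms is biased. That needs unequal loss or loss related to RSV risk, and the documents show neither. The shift could go in either direction.
- That the never-dosed problem carries into Season 2. Infants dosed in Season 1 have received study drug, so Protocol 4.1.6 keeps them under follow-up. In Season 2 the issue concerns only infants who leave during that season. With arms of about 50, each one is 2% of the denominator.

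**What to change.** Keep the crude ITT proportion with its exact interval as the main display. In SAP 3.5.1.1, 3.5.2.1 and their Season 2 counterparts, add by arm:

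- the Kaplan-Meier incidence at 150 days post Dose 1 of that season, with a 95% CI, among dosed infants, censored at last contact;
- a rule for deaths not due to RSV: either treat them as a competing event, using the cumulative incidence function, or state how they are handled (SAP 3.5.1 already counts RSV-caused deaths as events);
- the number of infants who left before Day 151 without an event, in the same table.

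The cost is SAP wording and one extra table from dates already collected. Incidences will be slightly higher and intervals slightly wider, and the estimate assumes that loss is unrelated to RSV risk, which the table should state.
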